**Historical Protocol Versions**

Version 1: 28JUN2018

Version 2: 12SEP2018

Version 3: 19MAR2019

Version 4: 29JAN2020

Version 5: 26MAR2021

## LIST OF ABBREVIATIONS

Abbreviation or Term 	Definition/Explanation
AE	Adverse event
AESI	Adverse events of special interest
ALT	Alanine aminotransferase
ANCOVA	Analysis of covariance
ANOVA	Analysis of variance
APTT	Activated partial thromboplastin time
AST	Aspartate aminotransferase
AV	Atrioventricular
β-HCG	Beta-human chorionic gonadotropin
BID	Twice daily
BLQ	Below limit of quantification
BMI	Body mass index
BP	Blood pressure
BUN	Blood urea nitrogen
Ca ++	Calcium
CBC	Complete blood count
CFR	Code of Federal Regulations
CHF	Congestive heart failure
CI	Confidence interval
Cl-	Chloride
CL cr	Creatinine clearance
C max	Maximum observed concentration
C min	Trough observed concentration
CNS	Central nervous system
CR	Complete response
CRF	Case report form
CT	Computed tomography
CTCAE	Common Toxicity Criteria for Adverse Events
CV	Coefficient of variation
CYP	Cytochrome P450
D/C	Discontinue
ECOG	Eastern Cooperative Oncology Group

Abbreviation or Term 	Definition/Explanation
eCRF	Electronic case report form
DLT	Dose Limiting Toxicity
ECG	Electrocardiogram
Eg	Exempli gratia (for example)
FACS	Fluorescence Activated Cell Sorting
FDA	Food and Drug Administration
FDG-PET	Fluorodeoxyglucose (FDG)-positron emission tomography (PET)
GCP	Good Clinical Practice
GFR	Glomerular filtration rate
GGT	Gamma glutamyl transferase
GLP	Good laboratory practice
HBsAg	Hepatitis B surface antigen
HBV	Hepatitis B virus
HCO 3 	Bicarbonate
HCV	Hepatitis C virus
HIV	Human immunodeficiency virus
HR	Heart rate
hr	Hour or hours
IC 50	Half maximal inhibitory concentration
i.e.	Id est (that is)
IEC	Independent ethics committee
INR	International normalized ratio
IRB	Institutional review board
IU	International unit
IV	Intravenous, intravenously
LDH	Lactate dehydrogenase
LLQ	Lower limit of quantitation
MedRA	Medical Dictionary for Drug Regulatory Activities
MRI	Magnetic resonance imaging
MRSD	Maximum recommended starting dose
MTD	Maximum tolerated dose
NOAEL	No-observed-adverse-effect level
NOEL	No-observed-effect-level

Abbreviation or Term 	Definition/Explanation
PD	Pharmacodynamic(s)
PFS	Progression Free Survival
PK	Pharmacokinetic(s)
PO	Per os (administered by mouth)
PR	Partial response
PT	Prothrombin time
PTT	Partial thromboplastin time
QC	Quality control
RBC	Red blood cell
QD	Once daily
QTc	QT interval corrected
QTcF	QT interval corrected using Fredericia equation
SAE	Serious adverse event
SD	Standard deviation or stable disease
SUSAR	Suspected Unexpected Serious Adverse Reaction
T 1/2	Terminal elimination half-life
T 3	Triiodothyronine
T 4	Thyroxine
T max	Time of maximum observed concentration
TID	Three times daily
TSH	Thyroid-stimulating hormone
ULN	Upper limit of normal
ULQ	Upper limit of quantitation
UV	Ultraviolet
WBC	White blood cell
WOCBP	Women of childbearing potential
WONCBP	Women of nonchildbearing potential

 All of these abbreviations may or may not be used in protocol.

## STUDY SUMMARY

Title	A Phase II Study of Rucaparib Monotherapy in Nonmetastatic, Hormone-Sensitive Prostate Cancer Demonstrating “BRCAness” Genotype.
Short Title	Rucaparib Nonmetastatic prOstAte with BRCAness (ROAR)
Protocol Number	IRB# 111833
IND	Exempt
Phase	Phase II
Design	This is a single arm, open label, phase II trial to assess efficacy of rucaparib.
Study Duration	Expected enrollment duration is 12 months, patients will remain on study treatment until PSA progression defined by PCWG3  . We estimate 2-3 years for total study duration.
Study Center(s)	This study will be conducted at the Huntsman Cancer Institute.
Objectives	
Primary Objective: To assess PSA progression free survival (PSA-PFS) . Patients will have PSA values measured every month.
 
Secondary Objectives
 
 
1. To assess the safety of rucaparib.
 
2. To assess the proportion of patients with a 50% reduction in PSA levels (PSA50) compared to the baseline value
 
3. To assess the proportion of patients with an undetectable PSA after initiation of PARP therapy.
 

Number of Subjects	15 evaluable subjects will be enrolled
Diagnosis and Main Eligibility Criteria	
 
1. Histologically proven adenocarcinoma of the prostate with BRCAness (defined as an alteration in one or more of the following genes: BARD1, BRCA1, BRCA2, BRIP1, CHEK1, CHEK2, FANCA, NBN, PALB2, RAD51C, RAD51D, RAD51, RAD51B based on soft tissue or liquid biopsy.
 
2. Rising PSA without radiographic evidence of metastatic disease and with PSA doubling time of <math>\leq 10</math> months.
 
3. ECOG/Zubrod score of 0-2.
 
4. Subject must not have received any prior systemic therapy for prostate cancer unless used in the context of definitive treatment for prostate cancer. Patients may have not received ADT treatment for longer than 24 months.
 

Study Product, Dose, Route, Regimen	
Rucaparib 600mg orally twice daily
 
No patients will be on ADT therapy either by surgical castration or with GnRH agonist or antagonist or on androgen synthesis blocker or androgen receptor antagonists during the study period.

Duration of administration	Subjects will remain on study treatment until unacceptable toxicity, PSA progressive disease (unless they meet the criteria for continued treatment post-progression as defined by section 6.4.1), or patient withdrawal.

Reference therapy	None
Statistical Methodology	
Primary Objective: The total sample size is 15 patients. The null hypothesis is that median PSA-PFS is 3 months. With an alternative hypothesis that median PSA-PFS is 12 months, a sample size of 15 provides 90% power at one-sided alpha = 0.05. The proportion of subjects who achieve PSA50 will be reported along with a 95% exact binomial confidence interval.
 
Descriptive analysis methods will be used to analyze tabulated safety characteristics. Kaplan-Meier methods will be used to assess the proportion of patients with an undetectable PSA after initiation of PARP therapy.

## 1 OBJECTIVES

### 1.1 Primary Objective and Endpoint

1.1.1 To assess PSA progression-free survival (PSA-PFS).

Endpoint: the levels of PSA will be monitored monthly for comparison to baseline levels until the time of PSA progression, as defined by Prostate Cancer Working Group 3 (PCWG3) criteria (See Appendix B).

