#### 6.2.3 Accountability and Compliance

Rucaparib tablets will be dispensed to the patient in sufficient quantity to last until Day 1 of the next treatment cycle. Patients will keep all unused tablets and containers (empty, partially used, and/or unopened) for accountability at the next visit.

Patients should take rucaparib doses as close to 12 hours apart as possible, preferably at the same times every day. If a patient misses a dose (i.e., does not take it within 4 hours of the scheduled time), the patient should skip the missed dose and resume taking rucaparib with the next scheduled dose. Missed or vomited doses should not be made up.

Patients will be instructed to record daily doses taken or not taken in a patient diary. Treatment with rucaparib is continuous and each cycle will comprise 28 days.

All study drugs will be stored at the Huntsman Cancer Institute Investigational Pharmacy in accordance with Good Clinical Practice (GCP) and GMP requirements and the instructions given by the clinical supplies department of the sponsor, and will be inaccessible to unauthorized personnel. The investigator, or a responsible party designated by the investigator, must maintain a careful record of the inventory and disposition of the agent.

An adequate record of receipt, distribution, and return of all study drugs must be kept in the form of a Drug Accountability Form. Subject compliance with the treatment and protocol includes willingness to comply with all aspects of the protocol, and to have blood collected for all safety evaluations. At the discretion of the principal investigator, a subject may be discontinued from the trial for non-compliance with follow-up visits or study drug.

Instructions on medication resupply and destruction will be made available to affected parties as applicable.

At the conclusion of the study, and, as appropriate during the course of the study, the Investigator will return all used and unused study drug, packaging, drug labels, and a copy of the completed drug accountability ledger to Clovis.

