8. If treatment is discontinued prior to PSA progression, PSA testing will continue throughout follow-up until PSA progression or start of another treatment. Patients who have PSA progression prior to discontinuing treatment do not need to have PSA testing performed during follow-up.
9. Rucaparib will be administered as described in Section 6.
10. Blood collection for biomarkers will be collected at screening, C3D1, C7D1, and confirmed PSA disease progression ( $\pm 7$  days), if applicable, or at EOT visit (whichever occurs first).

11. For patients enrolled with an intact prostate, urine collection for biomarkers will be collected at screening, C3D1, C7D1, and confirmed PSA disease progression ( $\pm$  7 days), if applicable, or at EOT visit (whichever occurs first).
12. Archival tissue will be collected at screening (if available). Archival tissue should not be cut until instructed by the central lab.
13. Genomic or genetic testing for 'BRCAness' will be confirmed with either blood or tissue based testing.
14. An optional fresh tissue biopsy may be obtained at PSA Progression Confirmation Visit ( $\pm$  28 days) for subjects with radiographic disease progression.
15. CT scans of the chest/abdomen and pelvis and NM bone scans will be done at the time of PSA Progression Confirmation Visit ( $\pm$  28 days) as defined in section 10.1.
16. Follow-up should occur every 90 days ( $\pm$  14 days) for 2 years following End of Treatment as per standard of care (section 9).
17. Coagulation Panel includes PT/INR, PTT.
18. The end of treatment visit should occur within +/-3 days of the decision to discontinue treatment. If this visit overlaps with a regularly scheduled visit, only the procedures listed in the calendar for the EOT visit will be performed.
19. To be performed only if the subject has completed hormone therapy. Screening testosterone may be performed within 84 days of study enrollment.
20. Only patients who have suspected PSA progression during a regular study visit will have testing to confirm PSA progression at their next regularly scheduled visit. **Before continuation of treatment after confirmed PSA progression, the patient must agree to sign the Treatment After Progression Informed Consent Form.** Patients may complete the assessments required for PSA progression in conjunction with the next regularly scheduled cycle visit or at EOT.

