## **9.5 Follow-up Evaluations Q 90 days ( $\pm$ 14 days)**

Survival follow-up, including survival status and post-study treatments. Follow-up may be conducted via phone call or record review if laboratory assessments are not required.

- Laboratory assessments:
  - If treatment is discontinued prior to PSA progression, PSA testing will continue throughout follow-up until PSA progression or start of another treatment. Patients who have PSA progression prior to discontinuing treatment do not need to have PSA testing performed during follow-up.

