# **10 CRITERIA FOR EVALUATION AND ENDPOINT**

## **10.1 Efficacy**

Patients must receive one full cycle of rucaparib and have PSA assessed after that cycle to be evaluable for efficacy. Patients who do not meet evaluable criteria will be replaced.

PSA levels will be monitored monthly while on treatment for comparison to baseline levels with the objective of assessing the proportion of patients with a 50% reduction in PSA levels (PSA50).

PSA progression-free survival (PSA-PFS) is defined as the time from study enrollment until the time of PSA progression as defined by PCWG3 criteria or death.

Patients who start another anti-cancer treatment prior to PSA progression or who complete one year of follow-up without PSA progression will have their data censored at that time point.

Overall survival is defined as the time from study enrollment until death. Survival will be monitored while on study and every 90 days for 2 years after study discontinuation.

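### PSA is promised monthly until progression, but men who stop rucaparib early are tested every 90 days, so their progression is dated about a month later on average

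*Combined protocol and SAP*

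**What the plan says.** **General statements.** For the primary endpoint, section 1.1.1 states that "the levels of PSA will be monitored monthly for comparison to baseline levels until the time of PSA progression". The study summary says, under the primary objective, "Patients will have PSA values measured every month". Neither is limited to time on treatment.

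**Detailed schedule.** On treatment, PSA is drawn on day 1 of each cycle, and section 6.2.3 says "each cycle will comprise 28 days"; the calendar allows ±3 days. After an early stop, section 9.5 (headed "Follow-up Evaluations Q 90 days") says "If treatment is discontinued prior to PSA progression, PSA testing will continue throughout follow-up until PSA progression or start of another treatment". Calendar note 8 repeats this rule. Note 16 gives the timing: "Follow-up should occur every 90 days", with a 14-day window either side, for 2 years. No section adds a monthly PSA after the End of Treatment visit.

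**Section 10.1.** It says "PSA levels will be monitored monthly while on treatment", but the rest of that sentence gives PSA50 as the purpose. PSA-PFS is defined separately there, without a testing frequency.

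**Dating and analysis.** Appendix B takes the first qualifying rise as the date, requires a confirming value at least 3 weeks later, and does not count rises in the first 12 weeks. Section 10.1 censors at the start of another anti-cancer treatment, or at one year of follow-up without progression. Section 11.2 uses Kaplan-Meier methods for PSA-PFS.

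**The concern.** The primary endpoint is read off a visit grid, and the grid becomes about three times coarser when a man stops before progression. His recorded time then depends partly on why and when he stopped, for example because he could not tolerate the drug. A coarser grid dates progression later on average. The trial has one arm and a fixed null median of 3 months, so no control group carries the same lag, and the error favours rucaparib.

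The general statements and the detailed schedule also cannot both be followed for these men. A reader of the objectives would take it that every man was followed monthly to progression.

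**Working it through.** **The plan's own figure.** Section 11.1 gives 90% power for N = 15, medians of 3 and 12 months, exponential times and one-sided alpha 0.05, without naming a test. One reading reproduces it. Three-month PSA-PFS is 0.50 under the null and 0.5^(3/12) = 0.841 under the alternative. The arcsine approximation gives Φ(2√15 × [arcsin√0.841 − arcsin√0.5] − 1.645) = 89.6%. The figure makes no allowance for visit spacing.

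**Gap lengths** (30.44 days per month).

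| | Nominal | Longest within window |
|---|---|---|
| On treatment | 28 days | 28 + 3 = 31 days (1.02 months) |
| End of Treatment PSA to first follow-up PSA | 90 days | 90 + 14 = 104 days (3.42 months) |
| Difference | 62 days (2.04 months) | 73 days (2.40 months) |

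If progression is equally likely anywhere in a gap, the mean lag is half the gap: 45 against 14 days. The difference is 31 days, or 1.02 months.

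The 2.0–2.4 months compares longest gaps and is not a strict bound for one man. The two grids drift out of step at later visits, and the largest single excess in the simulation below was 2.89 months. If follow-up windows are fixed from End of Treatment, two later visits can also be 118 days apart.

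**The 12-week rule.** Section 10.1 makes a man evaluable after one full cycle and a PSA. If he stops at day 28, his first follow-up PSA falls at day 28 + 90 = 118 (window 104–132), so at 3.4 months at the earliest. A later stop moves it later still. If he stops before week 12, his End of Treatment PSA falls where rises do not count. On a monthly schedule, the PSA at about day 84 (2.8 months) could count. That is the one scheduled value that could count before the null median.

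**Effect on the group.** The early-stop rate is assumed, because the documents give none. The simulation used N = 15, exponential times, 28-day against 90-day visits after stopping, and no censoring for new treatment.

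- *Mean under the null.* With 40% assigned to stop at cycles 1–6, only 20% stop before progressing, and the mean rises by 0.24 months without the 12-week rule or 0.29 with it. A quarter of that, for 10% assigned, is 0.06–0.07. Spreading stops over months 1–6 instead, without the rule, share affected × mean delay gives 0.043 × 1.185 = 0.05 (10% assigned), 0.085 × 1.173 = 0.10 (20%) and 0.139 × 1.171 = 0.16 (33%).
- *Pooled median.* It stays at 3.68 months under the null and 12.88 under the alternative. The one exception is 40% assigned with the 12-week rule, under the null: 3.68 to 3.88. Recorded times sit on visit dates, so the median moves only in steps.
- *Type I error.* The test was a one-sample exponential Wald test, z = √d × ln(estimated median/3), rejecting above 1.645, with d events, censoring at 12 months, stops over months 1–6 and no 12-week rule. Exact event times give about 3.4%. Monthly dating gives 6.2–6.6%. Ninety-day dating after stopping gives 7.3%, 7.8% and 8.9% with 10%, 20% and 33% assigned to stop.
- *Power.* Over 99% on either schedule with this test.

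**The case against.** The strongest reply is that the detailed schedule is deliberate. The calendar and section 9.5 expressly keep testing men who stop before progression, most follow-up for this endpoint is on treatment, and dating an event at detection is the usual convention. Monthly visits also date late, by up to 31 days. Men who start other treatment are censored, and the earliest stoppers, without a full cycle and a later PSA, are replaced. This stands. It limits the number of men affected and explains why the group effect is small, but it does not remove the conflict in the text or the direction of the error.

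Three stronger readings are tempting, and the documents do not support them.

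- A reader might infer that the schedule conflict makes progression 3.4 months late, longer than the null median. The 104 days is lag against a continuous clock, and it sets one man's worst case beside a group median.
- A reader might take section 10.1 as restricting PSA-PFS monitoring to time on treatment. The sentence concerns PSA50.
- A reader might express the mean shift as a share of the 3-month null median. Under the plan's exponential assumption, the matching null mean is 3/ln 2 = 4.33 months.

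The need for confirmation does not move the event date either, because the first rise is used. A confirming value some 90 days away leaves more time to start another treatment and be censored, but nothing in the documents allows that to be sized.

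**Conclusion.** The conflict is real, and its effect is small and directional. Men who stop before progression are dated about 1 month later on average than on a monthly schedule, and roughly 2.0–2.4 months at most by comparing gap lengths. Those who are evaluable and stop before week 12 cannot have progression recorded at a scheduled PSA before the 3-month null median.

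If 10–40% are assigned to stop early, the null mean rises by about 0.06–0.3 months, the pooled median is essentially unchanged, and type I error rises by one to three percentage points at the rates tested (10–33%). These figures rest on the assumed stop rate and timing, exponential times and an assumed test. The type I figures omit the 12-week rule, which delays recording on both schedules, so they show the contrast between schedules and not the trial's actual error rate. The point does not overturn the design. It deserves correction because the bias favours the drug, is tied to early stopping, and is cheap to address.

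**What to change.** 1. Reconcile section 1.1.1 and the study summary with the calendar (notes 8 and 16) and section 9.5, so that one PSA schedule for PSA-PFS after early stopping is stated throughout. Section 10.1 should refer to it beside the PSA-PFS definition.
2. Pre-specify an interval-censored sensitivity analysis of PSA-PFS, placing each event between the last non-qualifying and the first qualifying PSA. State how the 12-week rule sets the earliest possible bound.
3. State that PSA values drawn in routine care between the 90-day contacts will be collected and used to narrow those intervals.
4. Report how many men stopped before progression, and when.

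The cost is wording, one extra model fit and retrieval of existing results, with no added visits. The downside is a second estimate, possibly shorter and imprecise with 15 men. Fixing it in advance avoids choosing a method after open-label outcomes are known.

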### 1.2 Secondary Objectives and Endpoint

1.2.1 To assess the safety of rucaparib in patients with biochemically recurrent hormone-sensitive prostate cancer.

Endpoint: adverse events will be monitored regularly during patient enrollment and follow up to assess the toxicity of rucaparib using validated CTCAE v5.0 criteria.

1.2.2 To assess the proportion of patients with a 50% reduction in PSA levels (PSA50) compared to the baseline value at the time of study enrollment.

Endpoint: the levels of PSA will be monitored monthly for comparison to baseline levels.

1.2.3 To assess the proportion of patients with an undetectable PSA after initiation of PARP therapy at 6 and 12 months.

Endpoint: the levels of PSA will be monitored monthly for comparison to baseline levels to determine when PSA becomes undetectable.

1.2.4 To evaluate overall survival (OS) in nonmetastatic hormone-sensitive prostate cancer patients treated with rucaparib.

Endpoint: Subjects will be evaluated for survival using Kaplan-Meier estimation.

### 1.3 Exploratory Objectives and Endpoint

1.3.1 To evaluate exploratory biomarkers predictive of response and resistance to treatment with rucaparib.

Endpoint: blood and other tissue will be collected at baseline and during treatment to correlate clinical responses with various potentially predictive biomarkers.

1.3.2 To evaluate concordance between PSA-PFS and radiographic progression

Endpoint: levels of PSA will be monitored monthly and compared to the detection of any measureable new lesions by radiographic detection.

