## 8 STUDY CALENDAR

1 cycle = 28 days ( $\pm$  3 days)

Examination	Screening 	C1D1 	C(2+)D1 	PSA Progression Confirmation 	End of Treatment 	Follow-up 
Informed consent	X					
Treatment after PSA Progression ICF 				X		
Medical history	X					
Eligibility criteria 	X					
Vital signs	X	X	X	X	X	
Physical examination	X	X	X	X	X	
ECOG performance status	X	X	X	X	X	
Hematology 	X	X	X	X	X	
Chemistry 	X	X	X	X	X	
Lipid Panel 	X	X	X	X	X	
PSA 	X	X	X	X	X	X 
Urinalysis	X					
Coagulation Panel 	X					
Testosterone	X 					
ECG	X					
Adverse Event Assessment		X	X	X	X	
Concomitant Medication Review	X	X	X	X	X	
CT scans (c,a,p)	X			X 		
NM Bone Scans	X			X 		

Examination	Screening 	C1D1 	C(2+)D1 	PSA Progression Confirmation 	End of Treatment 	Follow-up 
Rucaparib administration 		X	X			
Blood for Correlative Studies 	X		X 	X 	X 	
Urine for Correlative Studies 	X		X 	X 	X 	
Archival Tissue for Correlative Studies 	X					
BRCAness Test 	X					
Optional biopsy 				X		
Survival Follow-up						X

1. All Pre-study/Screening procedures should be completed within 4 weeks of study enrollment. CT Scan and NM Bone scan do not need to be repeated if done within preceding 90 days of visit.
2. C1D1 procedures do not need to be repeated if screening procedures have been done within 7 days of start of treatment.
3. Cycles will continue at  $28 \pm 3$  days according to criteria in [Section 6.4](#).
4. Confirmation of BRCAness by previous result or prospective analysis of archival tissue or blood sample biopsy. If archival tissue is unavailable, a new biopsy will NOT be required.
5. Hematology includes CBC with differential and platelets.
6. Chemistry includes Albumin, Alkaline Phosphatase, Aspartate Aminotransferase, Alanine Aminotransferase, Total Bilirubin, Calcium, Carbon Dioxide, Creatinine, Chloride, Glucose, Potassium, Protein, Sodium, and Urea Nitrogen.
7. Lipid panel to consist of cholesterol, triglycerides, LDL cholesterol HDL Cholesterol, VLDL, and non-HDL Cholesterol.

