### **11.3 Exploratory Objectives**

Descriptive methods will be used to analyze the exploratory objectives. Circulating tumor DNA alterations and response category will be cross-tabulated. The mean and standard deviation of enumerated tumor cell characteristics will be reported separately for each response category. The mean and standard deviation at the time of radiographic progression will be reported for subjects with documented radiographic progression.

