**Table 1: Bone response assessment categories**

Bone Response	Definition
PD	2 new lesions, not flare, persistent
P Du	2 new lesions, but confirmation is required by the second scan. The temporary marker of PD should be updated to PD or non-PD upon subsequent scans. If P Du is determined on the last scan, sponsor should update to PD upon analysis.
Non-PD	At least 1 bone lesion present, but not enough to trigger PD.
NE	Status of bone lesions cannot be determined.
NED	No lesions are seen on bone scan (either none at baseline or all have resolved).

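### Post-baseline scans are triggered only by suspected PSA progression, so the concordance promised in 1.3.2 cannot be estimated; only radiographic status at PSA progression can

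*Combined protocol and SAP*

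**What the plan says.** Protocol section 1.3.2 sets the objective "To evaluate concordance between PSA-PFS and radiographic progression". Its endpoint is that "levels of PSA will be monitored monthly and compared to the detection of any measureable new lesions by radiographic detection". No scan interval is given there.

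The Study Calendar (section 8) marks CT and bone scans in two columns, Screening and PSA Progression Confirmation. The cells for on-treatment cycles, End of Treatment and Follow-up are blank. Footnote 15 states: "CT scans of the chest/abdomen and pelvis and NM bone scans will be done at the time of PSA Progression Confirmation Visit", with a ±28-day window, and section 9.3 repeats this. Footnote 20 restricts the visit: "Only patients who have suspected PSA progression during a regular study visit will have testing to confirm PSA progression". At screening, "CT Scan and NM Bone scan do not need to be repeated if done within preceding 90 days of visit" (footnote 1).

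Men who stop treatment before PSA progression keep having PSA tests in follow-up, with no imaging (footnote 8; section 9.5). After PSA progression, section 6.4.1 refers disease assessments back to the Study Calendar, which lists no further scans.

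Section 11.3 plans descriptive methods for the exploratory objectives. Its last sentence is "The mean and standard deviation at the time of radiographic progression will be reported for subjects with documented radiographic progression".

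Appendix B calls for a second bone scan at least 6 weeks later to confirm new bone lesions. Its Table 1 adds: "If P Du is determined on the last scan, sponsor should update to PD upon analysis".

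**The concern.** Concordance needs both outcomes observed in men with and without each event. Here one outcome decides whether the other is measured. The men who could show radiographic progression without PSA progression are those with no scheduled scan. A scheduled radiographic date can only fall near the PSA visit that triggered it.

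At stake is what may be concluded from objective 1.3.2. Close dates, or the finding that nearly every man with radiographic progression also had PSA progression, would reflect the scan schedule and say little about the disease. The primary and secondary analyses are not affected.

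**Working it through.** The plan gives no figure for this objective, so there is none to reproduce. Its only computed figure, 15 patients for 90% power (section 11.1), concerns PSA-PFS; only its sample size and medians are used here.

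**1. What the schedule lets one observe**

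| | Radiographic progression | No radiographic progression |
|---|---|---|
| PSA progression on treatment | observed at the triggered scan | observed at the triggered scan |
| PSA progression off treatment | no scheduled scan | no scheduled scan |
| No PSA progression | no scheduled scan | no scheduled scan |

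A few men with suspected but unconfirmed PSA progression might be scanned, so the last row need not be entirely empty. It is still not a sample of men without PSA progression. Kappa and overall agreement need that row. The first row alone gives P(radiographic progression | PSA progression, scanned). P(PSA progression | radiographic progression) is close to 100% by design.

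**2. Dates**

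Every scheduled post-baseline scan lies within 28 days of the confirmation visit. Appendix B dates PSA progression at the first qualifying rise. If that rise is confirmed at the next cycle visit (28 ± 3 days later), the scan falls between 28 − 3 − 28 = −3 days and 28 + 3 + 28 = 59 days from the PSA date. Lesions that appeared earlier and persist are seen at this scan, but their date and order are lost. The true date is known only to lie between the baseline scan and the triggered one.

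**3. How many men would contribute**

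Inputs: N = 15; exponential PSA-PFS with median m = 12 months (alternative) or 3 months (null), from section 11.1. All PSA-PFS events are treated as PSA progression, although section 10.1 also counts death.

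Expected number by month t = 15 × (1 − 2^(−t/m)):

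- m = 12, t = 12: 15 × (1 − 0.5) = 7.5
- m = 12, t = 24: 15 × (1 − 0.25) = 11.25
- m = 3, t = 12: 15 × (1 − 0.0625) = 14.06

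At the two olaparib medians cited in 11.1, 9.8 and 7.4 months, the 12-month numbers are 8.6 and 10.1. Men who progress off treatment must be subtracted from all of these.

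**4. Precision of the one estimable quantity**

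For x of n, the Clopper-Pearson limits are the 2.5% quantile of Beta(x, n − x + 1) and the 97.5% quantile of Beta(x + 1, n − x). Illustrations with n = 8:

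- 4/8: 0.157 to 0.843
- 2/8: 0.032 to 0.651
- 0/8: 0 to 0.369

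**5. Direction of bias if unscanned men were counted as negative**

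This was simulated with 200,000 patients, a Gaussian copula, PSA median 12 months and a 12-month horizon. Radiographic medians of 12, 24 and 48 months and copula correlations of 0, 0.5 and 0.9 are assumptions, not document figures.

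- Independent times: kappa 0.07 to 0.25, true value about 0.
- Correlation 0.9: kappa 0.02 to 0.43, true values 0.32 to 0.71.
- Across all scenarios, 57% to 92% of radiographic progressions within 12 months went unrecorded.
- Among men with both events, 15% to 36% of true date pairs lay within 28 days. The schedule puts every recorded radiographic date within 28 days of the PSA visit.

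Status agreement can thus be inflated or understated.

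**The case against.** Five points can be made for the plan.

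- **No agreement analysis is planned.** A reader might infer that the planned analysis would manufacture agreement. Section 11.3 does not support that: it plans only descriptive methods and no agreement or lag statistic. A negative scan at PSA progression would be recorded as discordant, and such scans could be common because men with metastases on conventional imaging are excluded at entry (5.2.1). This stands. Only the dates and P(PSA progression | radiographic progression) are largely fixed by the schedule.
- **The mean and SD sentence in 11.3.** It might be read as mean event time among progressors and struck out. It names no variable, and it follows a sentence on means and SDs of tumor-cell characteristics. It is most naturally the same summary taken at radiographic progression. This stands: the sentence should stay, with its variable named.
- **Bone confirmation.** One might infer that every unconfirmed bone progression becomes confirmed through the last-scan rule in Table 1. Appendix B itself calls for another scan, and the rule applies only if none follows. What survives is that the calendar does not schedule the scan Appendix B calls for. Since 1.3.2 refers to measurable new lesions while Appendix B records bone lesions as non-target only, over-calling is possible but not established.
- **Numbers scanned.** The one-year rule in section 10.1 censors PSA-PFS; it does not limit scanning. Half of 15 is therefore not a fixed expectation, and a range is needed.
- **Unscheduled scans** are not prohibited. True, but none are planned, and those done for clinical reasons would be selective.

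None of this restores the missing rows of the table.

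**Conclusion.** The point holds as a mismatch between objective and data collection. With scheduled post-baseline imaging tied to suspected PSA progression, the trial cannot estimate overall agreement, kappa, or the order or lag of the two events. It can estimate the proportion with radiographic progression among scanned PSA progressors, in roughly 7 to 14 men, with an interval as wide as 16% to 84% at 4 of 8.

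The counts assume the exponential medians in section 11.1 and no loss to off-treatment progression. The existence of the gap needs no such assumption, since it follows from the calendar. The direction of any bias in status agreement is undetermined.

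A reader might also suspect that the result is meant to support PSA-PFS as a surrogate for radiographic progression. The documents make no such claim. The objective is exploratory, so this is a desirable correction and no threat to the trial's main conclusions.

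**What to change.** 1. Restate 1.3.2, and add the matching analysis to 11.3, as the proportion of men with radiographic progression on the scan at PSA progression, among those scanned, with an exact 95% CI. Report the number of PSA progressors not scanned beside it.
2. State that no agreement, lead-time or surrogacy claim will be made.
3. Keep the mean and SD sentence in 11.3 and name its variable, probably tumor-cell characteristics.
4. Reconcile the second bone scan called for in Appendix B with the Study Calendar, which does not schedule it. In this analysis, report bone progression without a confirmatory scan separately from confirmed progression.

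The cost is wording in 1.3.2, 11.3 and Appendix B or the calendar. The restated analysis needs no extra scans. The downside is a narrower exploratory claim. Keeping agreement as the objective would instead need imaging that does not depend on PSA, a larger change that this point does not ask for.
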